## **5.8 Discontinuation of investigational product**

Patients may be discontinued from investigational product in the following situations:

### **5.8.1 Temporary discontinuation of a patient from investigational product**

Severe thrombocytopenia (platelet count <50,000/uL). Patients may restart study medication once the severe thrombocytopenia resolves.

Major surgery or other non-cardiovascular invasive procedures, see 5.6.9

Major bleeding, see 6.4.6.3

If possible, treatment with study medication should be resumed until the completion of the study (i.e. 30 days post randomisation).

### **5.8.2 Permanent discontinuation from study medication**

- Patient's decision: the patient is at any time free to discontinue treatment, without prejudice to further treatment.
- Incorrectly randomised patient in whom the inclusion/exclusion criteria violation would put the patient at undue risk
- Safety reasons as judged by the investigator (eg, clinically significant ventricular pauses, syncope related to bradycardia, persistent increase in serum creatinine level of clinical relevance, persistent, unexplained anaemia or thrombocytopenia
- Severe non-compliance to study protocol

All patients should remain in the trial and keep all visits whether they continue study medications or not.

### **5.8.3 Procedures for discontinuation of a patient from investigational product**

The patient once randomised is in the study for 30 days. If the patient is permanently discontinued from study medication, the patient should do the End of Treatment visit (V5). A follow-up contact (Visit 6) should be performed in order to collect all AEs/SAEs and suspected endpoints at 30 days post randomisation or 7 days after treatment.

A patient that decides to discontinue investigational product will always be asked about the reason(s) and the presence of any adverse events. If possible, they will be seen and assessed by an investigator(s). Adverse events will be followed up (See Sections 6.4.3 and 6.4.4); and all study drugs should be returned by the patient.

#### **For premature discontinuation from study medication:**

If premature discontinuation occurs at  $\leq 23$  days (Visit 5), then Visit 6 should be done between 28 and 32 days with SAE and suspected endpoints collected at that visit.

If premature discontinuation occurs between 24 and 27 days (Visit 5), then Visit 6 should be done 7 days following Visit 5 with SAE and suspected endpoints collected at that visit.

If a patient is withdrawn from study, see Section 5.9.

## **5.9 Withdrawal from study**

Randomised patients are at any time free to withdraw from study (investigational product and assessments), without prejudice to further treatment. Investigators must explain to any such patient so requesting termination of their participation, the importance to the trial and to themselves of their continued participation by keeping study visits. Should the patient insist on not returning for visits, the investigators should attempt to arrange telephone or other acceptable contact at visit times so that adverse events and study endpoints can be assessed. Every effort must be made to collect outcome data on every patient, within the boundaries of each patient's right to privacy and local regulations.

Randomised patient who refuses to sign the full version of the Informed Consent Form before first dose intake of active maintenance ticagrelor 90 mg will be withdrawn from the study. The patient will be asked to document her/his withdrawal on the Informed Consent Form used in the ambulance and the investigator will document this in the patient's medical records. No further efficacy data will be collected from the time of documented refusal. For safety purpose, the patient will be followed by the investigator for a period of 7 days after the last loading dose intake.

If, after having signed the full Informed Consent Form, the patient wished to withdraw from study, this is documented by consent withdrawal on the consent withdrawal page of the Informed Consent Form. The appropriate option should be ticked, and the page signed and dated by both the patient and the investigator, if possible. Such patients will always be asked about the reason(s) and the presence of any adverse events. They will be seen and assessed by an investigator. Adverse events will be followed up (See Sections 6.4.3 and 6.4.4) and all study drugs should be returned by the patient.

Withdrawn patients will not be replaced.

## **5.10 Patient lost to follow up**

No patient should be lost to follow up in this study. In the unlikely event that this does occur, repeated attempts will be made to locate and determine the vital status and occurrence of any MI or stroke for those patients who are considered initially lost to follow up and have not withdrawn consent. A patient will be classified as lost to follow up only if, he/she has failed to return for the required study visits and his/her vital status remains unknown despite multiple attempts to contact him/her via telephone, fax, email, certified letter.

## **6. COLLECTION OF STUDY VARIABLES**

The investigator will ensure that data are recorded in a timely fashion on the eCRF and in accordance with the instructions provided.

## **6.1 Recording of data**

The Rave Web Based Data Capture (WBDC) system will be used for data collection and query handling and SAE reporting. The electronic Case Report Forms (eCRF) will be completed in the hospital settings. The data collected in the source paper CRF at Visit 1 will be transferred in the electronic Case Report Forms by the hospital Study personnel. The investigator will ensure that data are recorded on the electronic Case Report Forms as specified in the study protocol and in accordance with the instructions provided.

The investigator ensures the accuracy, completeness and timeliness of the data recorded and of the provision of answers to data queries according to the Clinical Study Agreement.

Study personnel will be trained and responsible for entering data specified in the protocol into the WBDC system and according to the eCRF Instructions. When data have been entered reviewed, edited and Source Data Verification (SDV) performed by AstraZeneca representative, the data will be frozen to prevent further editing. The principal investigator will be notified to sign the eCRF electronically as per the eCRF instructions. A copy of the eCRF data will be archived at the study site.

## **6.2 Data collection and enrolment**

The visit schedule will be as follows:

- V1 between 30 minutes and 6 hours of onset of symptoms of acute MI: double blind loading dose of study medication will be given in pre-hospital settings/ambulance.
- V2: arrival in the Cath Lab.
- V3: Day 1, first day of active treatment period i.e. ticagrelor 90 mg twice daily.
- V4:48/72 hours post PCI..
- V5:Day 30,(28—32 days) End of Treatment (EOT) Visit.
- V6: Day 37 (for completer patients), follow up contact (telephone).  
In case of premature discontinuation, see section 5.8.3

### **6.2.1 Visit details**

#### **Visit 1 will occur in pre-hospital setting/ambulance**

After the inclusion and exclusion have been checked, the eligible patient will sign the full Informed Consent Form. If the patient is not able to give a written consent in pre-hospital settings, please refer to section 8.4.

The following assessments will be performed:

- 12-Lead ECG (collection of 2 print outs for central review), prior 1st study medication intake,
- Brief physical examination if a physician is present.
- Vital signs (heart rate and supine blood pressure (BP)).

The following data will be recorded:

- Date of Visit 1
- Location of care/ 1st medical contact
- Demography (age, date of birth, sex, race).
- Onset date and time of index event
- Date and time of qualifying ECG
- Date and time of 1st dose of study medication administration
- Specific relevant medical and surgical history and Killip class if physician present.
- Any AEs / SAEs or endpoints occurring after obtaining Informed Consent Form.
- Concomitant medication taken within 7 days of randomisation (ex: ASA or oral anti platelet therapy).

### **Transfer to Cath Lab**

The ambulance's personnel will hand over the study medication together with the patient to the Cath Lab's personnel.

### **Visit 2: will occur in Cath Lab of the hospital**

The Cath Lab's personnel will check that the individual patient study medication is present, the Informed Consent Form is signed, the source paper CRF or equivalent is completed and 2 print outs of the ECG done in pre-hospital settings are present.

If only the short form of the Informed Consent Form is signed then the full Informed Consent Form will be obtained as soon as the clinical situation allows it and before first dose intake of active ticagrelor 90 mg. If a patient is unable to read and sign due to critical condition, the full Informed Consent Form will be signed as soon as the clinical situation allows it, please refer to section 8.4.

In-hospital treatment must be given in the Cath Lab, before the ECG and pre-PCI angiography.

#### Cath Lab admission :

The following assessments will be performed:

- Brief physical examination if not performed in pre-hospital settings,
- Vital signs (heart rate and supine blood pressure (BP)), weight and height,
- 12-lead ECG post 2nd dose of study medication and prior angiography (collection of 2 print outs for central review). If possible, the same electrode patches and the same ECG machine used in pre-hospital settings should be used for this ECG, in order to collect the most accurate data.
- Local laboratory analysis for safety tests (clinical chemistry, haematology)
- Troponin I or T, (local analysis),
- Angiography should be performed at the arrival in the Cath Lab after second drug intake and ECG. The angiography data will be recorded for central review.

The following data will be recorded:

- Date of Visit 2 (i.e arrival in Cath Lab),
- Verify the eligibility criteria performed in pre-hospital settings and complete the full baseline assessments if needed.
- Verify the specific relevant medical and surgical history and complete the full baseline assessments if needed.
- All concomitant medications including use of relevant antiplatelet and anticoagulation medications 7 days prior to 1st dose of study medication intake,
- Date and time of administration of the 2nd dose of study medication.
- Date and time of 12-lead ECG
- Date of angiography and start-time, sheath insertion site (radial or femoral)

#### PCI:

- PCI: record date and start time (i.e time of 1st balloon inflation), type and number of stent implantation, thrombo-aspiration, bail out of GPIIb/IIIa receptor antagonists.

#### Post PCI:

- A post PCI angiography will be performed (the same CD/DVD containing both pre and post PCI imaging will be collected for central review)
- 12-lead ECG 60 minutes after PCI (collection of 2 print-outs for central review),
- Troponin (I or T) at 8 hours after PCI (local analysis).

AE/SAE, suspected endpoints and concomitant medication will be collected throughout hospitalisation.

### **Visit 3: onset of active treatment period**

After the loading dose period, all patients will receive active ticagrelor 90 mg BID as maintenance treatment during 30 days. Subsequent maintenance doses should be taken morning and evening, at approximately 12-hourly intervals, for the remainder of the treatment period. The 1st dose of active treatment should be taken 12 hours after blinded LD administered in Cath Lab.

The following assessments will be performed:

- Brief physical examination,
- Vital signs (heart rate, supine blood pressure (BP)),
- 12-lead ECG
- Local laboratory analysis for safety tests (clinical chemistry, haematology),
- Troponin (I or T) at 16 and 24 hours after PCI (local analysis).

AE/SAE, suspected endpoints and concomitant medication will be collected throughout hospitalisation.

### **Visit 4: 48/72 hours after PCI**

The following assessments will be performed:

- Brief physical examination,
- Vital signs (heart rate and supine blood pressure (BP)),
- 12-lead ECG,
- Local laboratory analysis for safety tests (clinical chemistry, haematology),
- Troponin (I or T), (local analysis).

Suspected endpoint events, AEs/SAEs and all medications will be recorded.

The bottle of active ticagrelor treatment will be given to the patient.

### **Visit 5: End of Treatment visit (EOT)**

This visit should take place at the end of the planned treatment period (30 days) or if the patient discontinues prematurely from the study treatment.

Suspected endpoint events, AE/SAE and current medications will be recorded. For patients reporting suspected endpoint events, SAEs, discontinuing study medication due to an AE, all peri-event medications will be recorded.

All remaining study medication will be returned and drug accountability performed.

The following assessments will be performed: see Visit 4.

After this 30 day period, it is up to the investigator to decide whether the patient should be maintained on ticagrelor as a component of dual antiplatelet therapy or continued antithrombotic therapy.

### **Visit 6: Safety Follow-up contact**

Completer patient will be contacted 7 days after the EOT visit. Any new SAEs will be recorded along with concomitant medication for SAE.

For patient who prematurely withdraws from study medication, a visit should occur at 30 days after randomisation and all suspected endpoints, procedures and new SAE (with its concomitant medications) should be collected. See section 5.8.3

## **6.3 Efficacy**

Clinical efficacy endpoints will be collected in the eCRF. These events will be identified using standard questioning of the patient at each visit, or by information that the investigator may receive as part of standard medical practice.

### **6.3.1 ECG and angiography**

#### **6.3.1.1 ECG**

ECGs should be performed according to local clinical practice to diagnose STEMI (Index event) and document the primary variable of the study.

ECGs should be standard 12-lead ECG, with a lead II rhythm strip, in the supine position. Particular attention will be given to the measurement of the ST-segment. Further details can be found in the Core Lab guidelines.

All original ECGs must be stored in the patient's medical record as source documentation.

ECGs will be recorded at the following time points:

**ECG evidence of STEMI:** Baseline qualifying ECG will be obtained in pre-hospital settings for the index event and eligibility in the study, prior 1st study medication administration. Due to the study design (randomisation within 6 hours and more than 30 minutes of onset of index event) the ECG assessment for inclusion into the study will be performed prior to obtaining informed consent form. These data will be recorded in the eCRF and utilised for the purposes of the study. This ECG will also be reviewed centrally and a double print-out is required.

**ECG performed in the Cath Lab** prior angiography and 60 minutes after PCI. These will be reviewed centrally and a double print-out is required. Only the date, hour and overall evaluation of the ECG recording will be captured in the eCRF.

ECG performed at Visit 3 , Visit 4 , Visit 5 : The recordings will be assessed locally and the data reported in the eCRF.

**Other ECG recordings:** ECG should be performed to document any re-occurrences of MI or recurrent cardiac ischaemia during the study.

If the investigator concludes that new ST elevation of  $\geq 1$  mm (0.1 mV) in at least 2 contiguous leads, development of new pathological Q waves on the ECG, new LBBB, ST-segment depression of  $\geq 0.5$  mm ( $\geq 0.05$  mV) in 2 or more contiguous leads, new or presumed new T-wave abnormalities - inversion of  $\geq 1$  mm (0.1 mV) in 2 or more contiguous leads indicative of ischaemia are present, then the ECG will be reported in the eCRF and copies of ECG traces will be included in any relevant 'Endpoint Package' sent to WCT endpoint office for central adjudication by the ICAC..

### **Central reading of ECG**

An independent central review of ECGs will be conducted. The ECG print outs at baseline, prior PCI and 60 minutes after PCI will be collected on an ongoing basis and sent to an AstraZeneca appointed Core Lab for central analysis. Results of this independent blind review will not be communicated to investigators, and the management of patients will be based solely upon the assessments conducted by the investigator.

#### **6.3.1.2 Angiography**

Angiography should be done immediately after arrival in Cath Lab, according to local clinical practice to document the co-primary flow variable of the study. Data acquisition: filming should be done for a sufficient duration (at least 10 seconds from the time of the contrast injection); 25 frames per second and 2 projections are preferred. Further details can be found in the core lab guidelines. The pre and post PCI angiography will be assessed locally and centrally. Only the date, time of the day and thrombus localization will be recorded in the eCRF.

### **Central reading of angiography**

An independent Central review of all coronary angiograms will be conducted. The imaging data pre and post PCI will be anonymised and transferred on the same CD/DVD. The

CD/DVD will be sent to an AstraZeneca appointed Core Lab for central analysis. The following will be measured:

- TIMI flow of MI culprit vessel at angiography, pre and post PCI
- Corrected TIMI frame count pre and post PCI angiography
- TIMI Myocardial Perfusion Grade pre and post PCI angiography

Results of this independent blind review will not be communicated to investigators, and the management of patients will be based solely upon the assessments conducted by the investigators.

### **6.3.2 Definition and follow up procedures for Suspected Clinical Endpoints**

For each suspected clinical endpoint, the investigator will complete information specific to that type of endpoint on the eCRF and compile relevant additional source information into an 'Endpoint Package', as described in the Endpoint and Bleeding Manual for Investigators. The Endpoint Package will be sent to the Independent Central Adjudication Committee (ICAC) for central adjudication except for death and bail out. The investigator should use the following definitions in assessing possible endpoint events.

#### **6.3.2.1 Myocardial Infarction**

##### **Definition:**

- (a) Recurrent MI within 18 hours of onset of the index MI New ST elevation of  $\geq 1$  mm (0.1 mV) in at least 2 contiguous leads and recurrent cardiac ischaemic symptomsa  $\geq 20$  minutes at restb.
- (b) Recurrent MI after 18 hours of onset of the index MI but before myocardial necrosis biomarkers have returned to normal Myocardial necrosis biomarker re-elevation (Troponin) defined as an increase of at least 50% over a previous value that was decreasing **and at least one of the following:**

- Recurrent cardiac ischaemic symptomsa  $\geq 20$  minutes at restb

or

- One of the following ECG changes
  - New ST elevation of  $\geq 1$  mm (0.1 mV) in at least 2 contiguous leads
  - Development of new pathological Q wavesc on the ECG
  - New LBBB.

(c) Patients with recurrent MI after myocardial necrosis biomarkers have returned to normal (excluding MI in patients undergoing PCI or CABG in the previous 24 hours). Elevation of myocardial necrosis biomarkers typical of acute MId with **at least 1 of the following:**

- Recurrent cardiac ischaemic symptomsa  $\geq 20$  minutes at restb
- Development of new pathological Q wavesc on the ECG
- ECG changes indicative of ischaemiac

or

- Pathological findings of an acute MI.

(d) MI within 24 hours after PCI:

- Troponin  $\geq 3x$  local laboratory upper normal limitf, and, if the pre-PCI Troponin was  $>ULN$ , both an increase by at least 50% over the previous value and documentation that Troponin was decreasing prior to the suspected recurrent MI (no symptoms are required)

or

- Development of new pathological Q wavesc on the ECG (no symptoms are required).

(e) MI within 24 hours after CABG:

- Troponin  $\geq 5x$  local laboratory upper normal limitf, and, if the pre-CABG Troponin was  $>ULN$ , both an increase by at least 50% over the previous value and documentation that Troponin was decreasing prior to the suspected recurrent MI and development of new pathological Q wavesc on the ECG (no symptoms are required)

or

- Troponin  $\geq 10x$  local laboratory upper normal limitf and, if the pre-CABG Troponin was  $>ULN$ , both an increase by at least 50% over the previous value and documentation that Troponin was decreasing prior to the suspected recurrent MI (no Q waves and no symptoms are required).

(f) For patients who die of suspected MI and for whom no myocardial necrosis biomarkers were obtained:

- The presence of new ST-segment elevatione and new cardiac ischaemic symptomsa

or

- Pathological evidence of an acute MI.

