### **4.1 Inclusion criteria**

For inclusion in the study patients should fulfill the following criteria:

1. Provision of Informed Consent (short form or full version of the Informed Consent Form) in pre-hospital settings (see section 8.4).

Due to the nature of the target disease and the study design the qualifying ECG will be performed in pre-hospital settings as normal procedure prior to obtaining patients informed consent. These data will be used for eligibility evaluation for this study.

2. Adult men and women aged 18 years or older. Women must not be of child-bearing potential (1 year post-menopausal or surgically sterile).

3. Symptoms of acute MI of more than 30 minutes but less than 6 hours
4. New persistent ST-segment elevation  $\geq 1$  mm in two or more contiguous ECG leads.

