## **4.2 Exclusion criteria**

Patients should not enter the study (or for exclusion criterion n° 2, not continue in study) if any of the following exclusion criteria are fulfilled:

1. Expected time to 1st PCI balloon inflation in the hospital, from the qualifying ECG is more than 120 minutes.
2. Patient's refusal to sign full version of the Informed Consent Form before first intake of active ticagrelor 90 mg BID
3. Concomitant oral or intravenous therapy with strong cytochrome P450 3A (CYP3A) inhibitors which cannot be stopped for the course of the study.
  - Strong inhibitors: ketoconazole, itraconazole, voriconazole, telithromycin, clarithromycin (but not erythromycin or azithromycin), nefazadone, ritonavir, saquinavir, nelfinavir, indinavir, atazanavir, over 1 litre daily of grapefruit juice.
4. Contraindication to ticagrelor (e.g. hypersensitivity to the active substance or to any of the excipients, active pathological bleeding, history of previous intracranial bleed, moderate to severe hepatic impairment).
5. Patient who has received a loading dose of clopidogrel, prasugrel or ticagrelor (commercial pack) for the index event or who are on chronic treatment of prasugrel, clopidogrel or ticagrelor (commercial pack)
6. Concomitant medication that may increase the risk of bleeding [e.g non steroidal anti-inflammatory drugs (NSAIDs), oral anticoagulant and / or fibrinolytics, planned or administered 24 hours before randomization]
7. Planned surgery during the study period
8. Any of the following conditions in the absence of a functioning implanted pacemaker: known SSS, second or third degree AVB, or documented syncope of suspected bradycardic origin.
9. Patient requiring dialysis
10. Known clinically important thrombocytopenia
11. Known clinically important anemia

12. Known pregnancy or lactation
13. Condition which may either put the patient at risk or influence the result of the study (e.g., cardiogenic shock or severe hemodynamic instability, active cancer, risk for non-compliance, risk for being lost to follow up)
14. Active involvement in the planning and/or conduct of the study (applies to both AstraZeneca staff and/or staff at the study site)
15. Previous randomisation in the present study
16. Participation in another clinical study with an investigational product or device study during the last 30 days or during the study.

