##### **6.4.7.2 Myocardial necrosis biomarkers**

The myocardial necrosis biomarkers (Troponin I or T) are required to document the index event and should be obtained to evaluate any recurrences of cardiac ischaemia. They will be analyzed locally for all patients to and will be collected at the following time points:

- In the Cath Lab (V2-pre PCI)
- And then at 8, 16 and 24 hours after PCI

Blood samples for Troponin measurement will also be collected whenever a patient is experiencing chest pain or cardiac event. The result will be part of the endpoint package for ICAC.

All local laboratory results and relevant reference ranges must be stored in the patient's medical record as source documentation.

For blood volume see Section 7.1

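### As written, MI criterion (d) does not exempt the index PCI, so the index infarct alone can meet it and dilute both secondary 30-day composites

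*Protocol*

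**What the plan says.** Section 6.3.2.1 lists six MI criteria. Three of them bear on the first day or so after the index event.

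- **Criterion (a)**, "a) Recurrent MI within 18 hours of onset of the index MI", needs new ST elevation together with recurrent ischaemic symptoms at rest.
- **Criterion (b)** runs from 18 hours until biomarkers have normalised. It needs a troponin re-elevation of at least 50% over a falling value, plus symptoms or an ECG change.
- **Criterion (d)**, "d) MI within 24 hours after PCI", has two alternative limbs. One is troponin of at least 3 times ULN "and, if the pre-PCI Troponin was" above ULN, with "both an increase by at least 50% over the previous value and documentation that Troponin was decreasing prior to the suspected recurrent MI" required as well. The other is new pathological Q waves "on the ECG (no symptoms are required").

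The definitions of terms add two relevant points. Footnote f treats indeterminate troponin values as abnormal. Footnote c accepts Q waves that are new or presumed new, without naming a reference ECG.

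The setting is as follows. Inclusion criterion 3 reads "Symptoms of acute MI of more than 30 minutes but less than 6 hours". Exclusion criterion 1 reads "Expected time to 1st PCI balloon inflation in the hospital, from the qualifying ECG is more than 120 minutes". Section 6.4.7.2 requires troponin before PCI, "And then at 8, 16 and 24 hours after PCI". Table 1, note (i), collects endpoints from consent, which precedes the index PCI. Section 2.2 places MI in both 30-day composites.

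**The concern.** Every patient enters with an evolving STEMI and is planned for PCI, so the ordinary course of the qualifying infarct unfolds inside the window of (d). The rule should separate that course from a second infarct. For patients with a raised pre-PCI troponin, the troponin limb does so. For patients sampled before troponin has risen it does not, and the Q-wave limb has no such test for anyone.

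The stake is the MI component of the first two secondary endpoints. Index infarcts counted as events would raise both arms' rates, shrink the difference between them and move the risk ratio towards 1.

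**Working it through.** **1. The plan's own figures.** The protocol gives no MI rate, composite rate or power for the composites, so there is no figure of that kind to reproduce. Its stated sample size concerns ST resolution. A pooled-variance chi-square without continuity correction, for 15% versus 21%, two-sided 2.5% and 80% power, gives 779 per group, as stated in section 12.3. Then 779 / 0.88 = 885.2, consistent with 1770 in total, or 885 per arm. MI is in neither co-primary endpoint, so these figures stand.

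**2. An uncomplicated index STEMI put through each rule** (no recurrent symptoms, no second infarct):

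| Course of the index infarct | (a), to 18 h | (b), after 18 h | (d), to 24 h after PCI |
|---|---|---|---|
| Pre-PCI troponin at or below ULN, then at least 3x ULN | not met | not met (no fall and re-rise) | **met** |
| Pre-PCI troponin above ULN, single rise and fall | not met | not met | not met on troponin |
| New Q waves within 24 h, any troponin | not met | not met (no re-elevation) | **met** |

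Criterion (c) expressly sets aside patients with PCI or CABG in the previous 24 hours. Criterion (d) has no comparable exclusion for the index PCI.

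**3. Timing.** Entry at more than 0.5 h and less than 6 h, with balloon inflation expected within 2 h of the qualifying ECG, puts the index PCI at roughly t = 0.5 to 8 h after onset. The window of (d) ends at t + 24. It overlaps (a) for 18 − t hours and runs t + 6 hours beyond it.

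- t = 0.5: ends at 24.5 h, overlap 17.5 h, 6.5 h beyond.
- t = 8: ends at 32 h, overlap 10 h, 14 h beyond.

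The 24 h post-PCI sample therefore always falls after hour 18. Giving (a) precedence would not close the gap alone; (b) would have to take precedence too.

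**4. Dilution, illustration only.** Assumptions, none from the protocol: true composite rates of 5% in-hospital versus 2.5% pre-hospital, and a share f of patients in each arm, equal across arms and independent of true events, whose index infarct alone meets (d).

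- Observed rate = p + (1 − p)f, so the absolute difference shrinks by the factor (1 − f).
- Power = Φ{[Δ√n − 1.96√(2p̄(1 − p̄))] / √(p₁(1 − p₁) + p₂(1 − p₂))}, with n = 885 and two-sided 5%.
- Share of in-hospital events that are false = (1 − 0.05)f / observed rate.

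For f = 10%: 0.05 + 0.95 × 0.10 = 0.145 and 0.025 + 0.975 × 0.10 = 0.1225. The ratio is 0.845, Δ = 0.0225 and p̄ = 0.13375. Then z = (0.0225 × 29.75 − 1.96 × 0.4814) / 0.4811 = −0.57, so power is 28%.

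| f | In-hospital | Pre-hospital | Risk ratio | Power | False share, in-hospital |
|---|---|---|---|---|---|
| 0 | 5.00% | 2.50% | 0.500 | 79% | 0% |
| 2% | 6.90% | 4.45% | 0.645 | 61% | 28% |
| 5% | 9.75% | 7.38% | 0.756 | 43% | 49% |
| 10% | 14.50% | 12.25% | 0.845 | 28% | 66% |
| 20% | 24.00% | 22.00% | 0.917 | 17% | 79% |

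With a smaller assumed effect, 5% versus 3.5%, power is 35% at f = 0 and 25%, 18%, 13% and 9% at the same values of f. The composites would then be weakly powered even with perfect classification.

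**The case against.** The best reply is that the protocol plainly means recurrent events. Criteria (a) to (c) are worded as recurrent MI, and the safeguard in (d) speaks of a suspected recurrent MI. Section 6.4.7.2 distinguishes documenting the index event from evaluating recurrences. Administrative Change 4 has investigators apply clinical judgment to suspected cardiac ischaemic events before recording an endpoint. Suspected MIs go to a central adjudication committee working under a written charter. A sensible adjudicator might never count an index infarct.

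That shows intent and may describe practice, but it does not change the rule. The word recurrent in (d) sits inside the conditional safeguard and reaches neither the normal-troponin branch nor the Q-wave limb. Section 6.3.2 tells investigators to use these definitions, and the abbreviations list describes endpoints as events specifically defined in the protocol. No section lets the committee set (d) aside. The manual and charter are not shown, so whether they close the gap is unknown.

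Three parts of the reply do stand. Footnote f narrows the troponin limb by treating indeterminate values as abnormal. Overlapping windows are not a contradiction in themselves: (a) and (b) can be read as governing the index episode, and what is missing is a statement that they do. And the protocol gives no frequency for normal pre-PCI troponin or early Q waves.

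**Conclusion.** The point holds as a defect of wording. Followed literally, (d) classes some index infarcts as new MIs and adds them to both secondary 30-day composites. If this happens equally in both arms, the effect is dilution towards no difference. Severity is moderate, because only secondary endpoints are touched; the co-primary tests, the Holm procedure and the sample size are not.

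The size is unknown. The table shows sensitivity and is not a forecast: every value of f and both true rates are assumed.

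A reader might infer three stronger things that the protocol does not support.

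- That the composites are in fact contaminated: this depends on literal application, and the documents that guide adjudication are not available.
- That false events must outnumber true reinfarctions: in the illustration, false events are 28% of in-hospital composite events at f = 2% and pass half only at f above about 5%.
- That the comparison is biased in favour of one arm: unequal f would bias it, but nothing in the protocol gives a direction or an amount.

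**What to change.** Reconcile (a), (b) and (d) for the index PCI so that the index infarct alone cannot qualify. Either of two wordings does this.

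1. State that (d) applies only to PCIs after the index procedure, with (a) governing up to 18 hours from onset and (b) thereafter. The price is that a symptom-free peri-procedural MI after the index PCI, within 18 hours of onset, is no longer counted.
2. Keep (d) for the index PCI, but there make the fall followed by a rise of at least 50% unconditional, and do not let Q waves qualify on their own. The price is sensitivity. With a normal pre-PCI value and only the routine samples, a fall can first be seen at 16 hours and a re-rise at 24 hours.

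The choice is a matter of endpoint design for the Executive Committee. In either case, name the reference ECG against which Q waves are judged new, and check that the endpoint manual and adjudication charter say the same.

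The cost is wording in section 6.3.2.1, handled as a protocol change under section 8.5, plus any alignment of those two documents. No new data are needed: the troponins and ECGs are already scheduled, and symptoms are part of the existing endpoint reporting. MIs already adjudicated under (d) after an index PCI should be reviewed again, blinded, under the settled rule.
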